9.2.2.2. Overall Survival

The primary analysis of OS is event-driven and will be conducted after at least 368 deaths have been observed in the ITT population ([Section 9.1.1](#)) for the experimental and control arms.

Hypothesis testing between the two treatment arms will be performed using the stratified log-rank test with a 2-sided α level of significance (the α level will be defined per [Section 9.5](#)). The stratification factors will be the same as those used to stratify the randomization.

The median duration of OS and the associated 95% and 1- α % CI for each treatment arm will be estimated using the Kaplan-Meier method. The HR with 95% and 1- α % CIs will be estimated using a Cox regression model and will include the same stratification factors described above.

Details of interim analyses of OS are provided in [Section 9.8](#).

At any analysis of OS (interim or primary), if the p-value for the stratified log-rank test is statistically significant and the HR ($\lambda_{\text{cabozantinib + atezolizumab}} / \lambda_{\text{sorafenib}}$) is < 1 , the null hypothesis of no difference in OS between the two treatment arms will be rejected and it will be inferred that OS is superior in the group receiving cabozantinib + atezolizumab compared with the group receiving sorafenib.

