9.3.1. Progression Free Survival (PFS) per BIRC between Single-Agent Cabozantinib and Control Arms

The analysis of PFS as a secondary endpoint is event-driven and will be conducted after at least 283 events have been observed in the ITT population (see [Section 9.1.1](#)) for the single-agent cabozantinib and control arms. It is designed to include progression events as determined by the BIRC per RECIST 1.1. General censoring rules as described in [Section 9.2.2.1](#) will be applied.

Hypothesis testing between the two treatment arms will be performed using the stratified log-rank test at the 2-sided α level (the α level will be defined per [Section 9.5](#)) in the ITT population, provided the null hypothesis for either PFS or OS is rejected in favor of the experimental arm (cabozantinib + atezolizumab) as described in [Section 9.5](#). The stratification factors will be the same as those used to stratify the randomization (see [Section 3.3](#)).

The median duration of PFS and the associated 95% and 99% CIs for each treatment arm will be estimated using the Kaplan-Meier method. The HR with 95% and 99% CIs will be estimated using a Cox regression model and will include the same stratification factors described above.

In the secondary analysis of PFS, if the p-value for the stratified log-rank test is statistically significant and the HR ($\lambda_{\text{cabozantinib}} / \lambda_{\text{sorafenib}}$) is < 1 , the null hypothesis of no difference between the two treatment arms in PFS will be rejected and it will be inferred that PFS is superior in the group receiving single-agent cabozantinib compared with the group receiving sorafenib.

One interim analysis of secondary PFS is planned at approximately 67% information fraction. Details are provided in [Section 9.8](#).

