9.5. Control of Type I Error

Inflation of Type 1 error associated with testing of multiple primary endpoints and a secondary efficacy endpoint (PFS between single-agent cabozantinib and control) will be controlled by a modified Bonferroni procedure, a gatekeeping technique, and the fallback method (FDA 2017). Initially, the study-wise 2-sided alpha of 5% will be unequally allocated between primary endpoints PFS (1%) and OS (4%). The secondary PFS endpoint will be tested at the 1% level only if the primary PFS test is successful. If the null hypotheses are rejected for both the primary and secondary PFS endpoints, the 1% alpha for PFS will be reallocated to OS, allowing it to be tested at the 5% level.

Two interim analyses of OS are planned at the 33% and 66% information fractions (the first interim will coincide with the primary analysis of PFS and will be performed only if the null hypothesis for PFS is rejected and is expected to occur at approximately the 33% information fraction). One interim analysis is planned for secondary PFS endpoint contemporaneous with the primary PFS analysis with anticipated information fraction of 67%. Type 1 error associated with interim analyses will be controlled using Lan-DeMets O'Brien-Fleming (LD-OF) alpha-spending functions based upon a 4% total alpha allocation for OS and 1% for secondary PFS.

The testing and alpha reallocation are elucidated below.

First, test primary PFS at the 1% level. Then:

1. If primary PFS is significant:
 - a. Re-allocate its 1% alpha to secondary PFS per the fallback method.
 - b. Conduct interim analysis of OS at 33% per LD-OF with 4% total alpha
 - c. Conduct interim analysis of secondary PFS endpoint at 67% per LD-OF with 1% alpha.
 - i. If interim analysis of secondary PFS is significant:
 - Re-allocate its 1% alpha to OS
 - Conduct interim analysis of OS at 66% per LD-OF with 5% alpha
 - No further inferential testing of secondary PFS will be performed.

- ii. If interim analysis of secondary PFS is not significant:
 - The final analysis of secondary PFS will be conducted at an alpha of 0.0096.
 - The alpha of subsequent OS analyses will be dependent on the timing and result of the final secondary PFS analysis.

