^d The interim analysis at 66% information fraction will be conducted at 4% alpha level if it occurs prior to the secondary PFS analysis. It will be conducted at 4.96% alpha level if it happens after the null hypothesis for secondary PFS is rejected at the time of final analysis. It will be conducted at 5% alpha level only if the null hypothesis for secondary PFS is rejected at the interim analysis.

Rejection of the null hypotheses for OS at the first interim analysis at about 33% information is not expected: it is designed primarily as an administrative analysis, expected to coincide with the primary analysis of PFS, and will be performed only if the null hypothesis for PFS is rejected.

Should the timing of the first interim analysis (IA1) of OS trend towards an information fraction much higher than expected (eg, due to faster-than-expected deaths or slower-than-expected PFS events), the interim analyses of OS will be conducted as follows:

OS IA1 IF	Proceed as	Rationale
< 50%	perform IA1 and IA2 as planned above	similar conditions to original plan
50 to < 66%	
 perform IA1 at time of primary PFS, irrespective of whether PFS null hypothesis is rejected or not Conduct IA2 at 80% IF (instead of 66%) 	
 Higher than expected information for OS negates administrative nature of the analysis. Preserves two interim analyses as planned with reasonable intervals between them
≥ 66%	perform a single interim analysis at 66% IF, irrespective of timing or results of primary PFS analysis.	Information fraction meets or exceeds that of planned analysis at 66%

IA1, first interim analysis; IA2, second interim analysis; IF, information fraction; OS, overall survival

An interim analysis of secondary PFS is planned contemporaneously with the primary PFS analysis and will be conducted only if the null hypothesis for primary PFS is rejected. It is anticipated to be at approximately 67% information fraction based on a total alpha of 1%. At this fraction, the critical p-value is 0.0096, and the maximum HR to reject the null hypothesis is 0.626.

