7.1.1.6 Primary Analysis

The timing of this analysis is event-driven, and it will be conducted after at least 257 events have been observed in the PITT population. It is designed to include progression events as determined by the BIRC per RECIST 1.1. Clinical deterioration determined by the investigator will not be considered progression events. The actual number of events at the time of analysis may be higher than 257 due to the logistics of estimating event counts in an ongoing multicenter clinical study and predicting cutoff dates for analysis.

The hypothesis testing between experimental arm (cabozantinib + atezolizumab) compared to the control arm (sorafenib) will be performed using the stratified log-rank test with a 2-sided $\alpha=0.01$ level of significance. The stratification factors are as described in Section 2.4 and the values used for analysis will be those recorded in the IRT.

The median duration of PFS along with the associated 99% and 95% confidence intervals (CI) for each study treatment arm will be estimated using the Kaplan-Meier method. The stratified hazard ratio (HR) and its 99% and 95% CI will be estimated using a Cox proportional-hazard model with treatment group as the independent variable using the same stratification factors as were used for the log-rank test.

If the p-value for the stratified log-rank test is less than the critical value for rejecting the null hypothesis and the HR ($\lambda_{\text{cabozantinib + atezolizumab}} / \lambda_{\text{sorafenib}}$) is < 1 , the null hypothesis of no difference between the two study treatment arms will be rejected and it will be inferred that duration of PFS is greater in the experimental arm (cabozantinib + atezolizumab) compared to the control arm (sorafenib).

The unstratified versions of all the above analyses will also be conducted.

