7.1.2.5 Primary Analysis

The timing of this analysis is event-driven and it will be conducted after at least 368 deaths (overall survival events) have been observed in the experimental and control arms in the ITT population. The actual number of events at the time of analysis may be higher than 368 due to

the logistics of estimating event counts in an ongoing multicenter clinical study and predicting cutoff dates for analysis.

The hypothesis testing between the experimental arm (cabozantinib + atezolizumab) compared to the control arm (sorafenib) will be performed using a 2-sided stratified log-rank test. Please see Section 7.2 for details regarding the allocation of overall Type I error (α -level). The stratification factors are as described in Section 2.4 and the values used for analysis will be those recorded in the IRT.

Additionally, up to two interim analyses of OS are planned at approximately the 33% (conditional on positive PFS endpoint inference) and 66% information fractions. The critical p-values (and observed HR) for testing these interim hypotheses will be based on Lan-DeMets O'Brien-Fleming alpha-spending function. The overall α to be spent on testing the duration of OS via the use of a spending function will as described in Section 7.2. The actual critical values for each OS analysis will depend upon the true number of events observed at conduct of each analysis. Details are provided in Section 7.3.

The median duration of OS along with the associated $(1-\alpha)$ % and 95% confidence intervals (CI) for each study treatment arm will be estimated using the Kaplan-Meier method. The stratified hazard ratio (HR) along with the associated $(1-\alpha)$ % and 95% CIs will be estimated using a Cox proportional-hazard model with treatment group as the independent variable using the same stratification factors as were used for the log-rank test.

If at any OS analysis (interim or primary) the p-value for the stratified log-rank test is less than the critical value for rejecting the null hypothesis and the HR (λ cabozantinib + atezolizumab/ λ sorafenib) is < 1 , the null hypothesis of no difference between the two study treatment arms will be rejected and it will be inferred that duration of OS is greater in the experimental arm (cabozantinib + atezolizumab) compared to the control arm (sorafenib).

The unstratified versions of all the above analyses will also be conducted.

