7.4 Secondary Efficacy Endpoint

7.4.1 Progression Free Survival (PFS) per BIRC between Single-Agent Cabozantinib and Control Arms

The secondary efficacy endpoint for this study is PFS per BIRC between single-agent cabozantinib and the control arms in the ITT population. The timing of this analysis is event-driven, and it will be conducted after at least 283 events have been observed in the two arms. Formal hypothesis testing is planned for this endpoint following the same methodology as outlined in Section 7.1.1.6. One interim analysis of secondary PFS is planned, to be

contemporaneous with the primary PFS analysis, at approximately the 67% information fraction (Section 7.3)

A supportive analysis of PFS per INV will also be performed on the ITT population.

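### The alpha-labelled hazard-ratio intervals are not matched to the interim tests, so at an interim look one can exclude 1 although the test has failed

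*Protocol*

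**What the plan says.** **Secondary PFS.** Protocol 9.3.1 plans the final analysis at 283 events and states the interval levels once: "The HR with 95% and 99% CIs will be estimated using a Cox regression model". It then adds "One interim analysis of secondary PFS is planned at approximately 67% information fraction" and refers to 9.8 for details. Neither section gives an interval level for that interim. SAP 7.4.1 says "Formal hypothesis testing is planned for this endpoint following the same methodology as outlined in Section 7.1.1.6", and SAP 7.1.1.6 reads "The stratified hazard ratio (HR) and its 99% and 95% CI will be estimated". That section was written for primary PFS, which has a single look at the 1% level.

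**Spending.** Protocol 9.5 applies Lan-DeMets O'Brien-Fleming spending "based upon a 4% total alpha allocation for OS and 1% for secondary PFS". For the secondary PFS interim, Protocol 9.8 prints a critical p of 0.0096 and states that "the maximum HR to reject the null hypothesis is 0.626". Protocol 9.5 gives 0.0096 as the level of the final secondary PFS test. SAP 7.3 prints no boundary for this interim.

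**OS.** Protocol 9.2.2.2 plans 95% and 1-alpha intervals, with alpha taken from 9.5. SAP 7.1.2.5 plans the same pair. It introduces alpha as the overall type I error and calls the per-look thresholds critical p-values: "The actual critical values for each OS analysis will depend upon the true number of events observed at conduct of each analysis". With 4% total alpha, both documents print critical p-values (and HRs) of 0.00011 (0.478), 0.00867 (0.701) and 0.03728 (0.794) at 33%, 66% and 100% information.

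Neither document specifies a repeated or look-adjusted interval.

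**The concern.** A 99% interval beside a 1% test, or a 96% interval beside a 4% test, tells the reader that interval and test agree. That is true for a single look, as in primary PFS. Under group-sequential testing the interim threshold is much stricter than the total alpha, so an interval at the total-alpha level can exclude 1 when the boundary has not been crossed.

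The secondary PFS interim and the first OS interim are planned alongside the primary PFS readout. If either fails, testing of that endpoint continues. An alpha-labelled interval excluding 1 could then stand beside a formally negative interim result in an open-label trial. Protocol 1.5.2 also makes the secondary PFS comparison the basis for establishing what cabozantinib contributes to the combination.

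**Working it through.** **Inputs.** Secondary PFS: 283 events, 1:1 allocation, design HR 0.65, total alpha 1%, looks at 67% and 100%. OS: 368 deaths, 2:1 allocation, design HR 0.69, total alpha 4%, looks at 33%, 66% and 100% (Protocol 9.5, 9.7, 9.8; SAP 2.3, 7.3).

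**Formulas** (normal approximation to the stratified log-rank and Cox results). SE of log HR = 1/√(D·p·(1−p)), which is 2/√D at 1:1 and 1/√(2D/9) at 2:1. A threshold z corresponds to an observed HR of exp(−z·SE).

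**Reproducing the printed secondary PFS boundary.**
- D = 0.67 × 283 = 189.6, SE = 2/√189.6 = 0.1452.
- Spending per side at 67% = 2·[1 − Φ(2.807/√0.67)] = 0.000605, so z = 3.2365 and two-sided p = 0.0012.
- HR = exp(−3.2365 × 0.1452) = 0.625 (printed 0.626).
- At the final look the same method gives p = 0.0096 and HR 0.735, both as printed.
- The printed interim p of 0.0096 does not reproduce. At 190 events it would correspond to HR 0.686, whereas HR 0.626 corresponds to p of about 0.0013.

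**Secondary PFS interim: interval against test.**
- The 99% interval excludes 1 at HR ≤ exp(−2.5758 × 0.1452) = 0.688.
- At true HR 0.65: P(HR ≤ 0.688) = Φ(0.390) = 0.652 and P(HR ≤ 0.625) = Φ(−0.270) = 0.394. The difference is 0.258, about 26% (25% with the printed 0.626).
- Example: an observed HR of 0.65 has p = 0.003 and fails the test. Its 99% interval is 0.45 to 0.94; the interval at the look's own level is 0.41 to 1.04.

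**OS at 66%, reading alpha as 4%.**
- D = 0.66 × 368 = 242.9, SE = 1/√53.97 = 0.1361.
- The 96% interval excludes 1 at HR ≤ exp(−2.0537 × 0.1361) = 0.756. The printed boundary is 0.701; recomputed spending gives 0.698.
- At true HR 0.69: P(HR ≤ 0.756) = 0.749 and P(HR ≤ 0.698) = 0.535. The difference is 0.214, about 21% (20% with the printed 0.701).
- Example: an observed HR of 0.73 has p = 0.021 and fails. Its 96% interval is 0.55 to 0.97; at 1 − 0.00867 it is 0.51 to 1.04.

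**Final looks.** Secondary PFS: 0.736 for the 99% interval against 0.735 for the test. OS: 0.797 for the 96% interval against 0.794.

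These probabilities treat each look on its own. They are not conditional on primary PFS having been rejected.

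**The case against.** **No decision depends on an interval.** This stands. The rule in Protocol 9.2.2.2 begins "At any analysis of OS (interim or primary), if the p-value for the stratified log-rank test is statistically significant", and 9.3.1 is parallel. Critical values are prespecified and recalculated at the actual information. A reader might infer that type I error is inflated; it is not.

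**Protocol 9.3.1 may describe only the final analysis.** On that view the interim level is unspecified rather than set at 99%. The text allows this. Even so, 99% and 95% are the only levels offered for this endpoint, and a programmer following the plan has nothing else to use.

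**With the printed p of 0.0096, the 99% interval would almost match the interim test** (HR 0.688 against 0.686). That is correct arithmetic, but the printed p conflicts with the HR of 0.626 beside it and with 1% O'Brien-Fleming-type spending. The contradiction needs correcting in its own right and does not justify the 99% level.

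**For OS, alpha could mean the level of the look.** The 1-alpha interval would then already match. Protocol 9.5 does once use alpha for a single look (0.0096). A reader might infer that no OS interim interval corresponds to its test; the documents do not establish that, because alpha is undefined for interim intervals. SAP 7.1.2.5 favours the overall-alpha reading.

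**Larger figures are available but do not carry over.** Counting all three OS looks under no effect, at least one 96% interval excludes 1 in roughly 9% of trials. That count includes the 33% look unconditionally. In the base plan this look is run only after primary PFS is rejected, and it is described as mainly administrative. Without it the figure is about 6%. Nor is a 96% or 99% interval too narrow as a pointwise interval at a fixed look; it simply does not correspond to the sequential test.

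**Conclusion.** The point holds as a reporting and interpretation defect that should be corrected. For secondary PFS, the only planned levels do not match the interim test: observed HRs between 0.626 and 0.688 give a 99% interval that excludes 1 with a failed test, in about 26% of trials at a true HR of 0.65. For OS the level at an interim is undefined. On the more natural reading, the 66% look has the same problem between 0.701 and 0.756, in about 21% of trials at a true HR of 0.69. The figures assume the planned information fractions, the normal approximation and 4% total alpha for OS. The secondary PFS size also assumes that the printed HR of 0.626, not the printed p of 0.0096, is the intended boundary, as the spending function indicates. Primary PFS is not affected.

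**What to change.** In Protocol 9.2.2.2 and 9.3.1 and SAP 7.1.2.5 and 7.4.1, state one rule: at each look the alpha-matched HR interval has level 1 minus the two-sided critical p actually used at that look, recalculated at the actual information fraction. Write it as a rule rather than as fixed percentages, because the SAP addendum spends alpha on the information available at the analysis. At the planned fractions, with 4% for OS, the levels would be:

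- OS at 66%: 1 − 0.00867 = 99.13%
- OS final: 1 − 0.03728 = 96.27%
- Secondary PFS interim: about 99.88%
- Secondary PFS final: 1 − 0.0096 = 99.04%

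Keep the 95% interval but label it descriptive at every look. It excludes 1 even more readily (HR 0.766 at the OS 66% look), so the label is needed. In Protocol 9.8, correct the interim critical p for secondary PFS so that it agrees with the HR beside it.

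The cost is about a sentence per section, one corrected figure and one program parameter. The price is wider interim intervals.

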9.4. Additional Endpoints

Details of the planned analyses of these endpoints will be provided in the SAP:

- ORR, TTP, and DOR per RECIST 1.1 by BIRC and Investigator
- Evaluation of radiographic response per modified RECIST (mRECIST)
- Safety through the evaluation of AEs, including irAEs and other AESIs
- Characterization of the PK of cabozantinib in subjects with previously untreated HCC
- Immunogenicity of atezolizumab given in combination with cabozantinib
- Change in serum AFP from baseline

- Correlation of biomarker analyses with clinical outcomes
- Health-related quality of life (HRQOL) as assessed by the EuroQol Health questionnaire instrument (EQ-5D-5L)
- Healthcare resource utilization

9.5. Control of Type I Error

Inflation of Type 1 error associated with testing of multiple primary endpoints and a secondary efficacy endpoint (PFS between single-agent cabozantinib and control) will be controlled by a modified Bonferroni procedure, a gatekeeping technique, and the fallback method (FDA 2017). Initially, the study-wise 2-sided alpha of 5% will be unequally allocated between primary endpoints PFS (1%) and OS (4%). The secondary PFS endpoint will be tested at the 1% level only if the primary PFS test is successful. If the null hypotheses are rejected for both the primary and secondary PFS endpoints, the 1% alpha for PFS will be reallocated to OS, allowing it to be tested at the 5% level.

Two interim analyses of OS are planned at the 33% and 66% information fractions (the first interim will coincide with the primary analysis of PFS and will be performed only if the null hypothesis for PFS is rejected and is expected to occur at approximately the 33% information fraction). One interim analysis is planned for secondary PFS endpoint contemporaneous with the primary PFS analysis with anticipated information fraction of 67%. Type 1 error associated with interim analyses will be controlled using Lan-DeMets O'Brien-Fleming (LD-OF) alpha-spending functions based upon a 4% total alpha allocation for OS and 1% for secondary PFS.

The testing and alpha reallocation are elucidated below.

First, test primary PFS at the 1% level. Then:

1. If primary PFS is significant:
 - a. Re-allocate its 1% alpha to secondary PFS per the fallback method.
 - b. Conduct interim analysis of OS at 33% per LD-OF with 4% total alpha
 - c. Conduct interim analysis of secondary PFS endpoint at 67% per LD-OF with 1% alpha.
 - i. If interim analysis of secondary PFS is significant:
 - Re-allocate its 1% alpha to OS
 - Conduct interim analysis of OS at 66% per LD-OF with 5% alpha
 - No further inferential testing of secondary PFS will be performed.

- ii. If interim analysis of secondary PFS is not significant:
 - The final analysis of secondary PFS will be conducted at an alpha of 0.0096.
 - The alpha of subsequent OS analyses will be dependent on the timing and result of the final secondary PFS analysis.
 - The second interim analysis and the final for OS will be conducted per LD-OF with 4% alpha, if the second interim analysis occurs prior to the final analysis for secondary PFS, or, if it occurs after the final secondary PFS analysis where the final secondary PFS fails to reject its null hypothesis.
 - The subsequent OS analyses will be conducted per LD-OF with 4.96% alpha if it occurs after the rejection of the null hypothesis for secondary PFS.
- d. Conduct interim and final analyses of OS with appropriate alpha as determined above

2. If primary PFS is not significant:

- a. Secondary PFS analysis cannot be conducted
- b. Conduct interim and final analyses of OS per LD-OF with 4% total alpha
 - i. If OS is not significant at final analysis, procedure ends

All other statistical evaluations of efficacy will be considered exploratory.

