9.8. Interim Analyses

The number of events required to evaluate OS is based upon assumptions currently available and provides high power to detect the smallest clinically meaningful difference in OS under these assumptions. However, as there is uncertainty in the assumptions, interim analyses provide an opportunity to stop the trial early if the treatment benefit of the experimental arm is larger than expected, potentially allowing the new regimen to become available sooner to this patient population.

Two interim analyses of OS are planned at approximately the 33% and 66% information fractions based on a total alpha of 4%. However, if the null hypotheses are rejected for both the primary and secondary PFS endpoints, the 1% alpha for PFS will be reallocated to OS per the fallback method. As a consequence, the final OS analysis will employ critical values from the spending function at the 5% level. The alpha level of the interim analysis at 66% will be dependent on the timing of the interim analysis and the results of secondary PFS interim and final analyses. The second interim analysis of OS at 66% information fraction can be conducted at the overall 5% alpha level only if it occurs after the null hypothesis for the secondary PFS is rejected at the interim analysis.

Details and boundaries for these interim and the final analyses are shown in the table below:

	Critical Values for Testing OS					
	4.0%		4.96%		5.0% ^a	
OS alpha total	Critical p-value	HR to reject	Critical p-value	HR to reject	Critical p-value	HR to reject
33% ^b	≤ 0.00011	≤ 0.478	NA ^c	NA ^c	≤ 0.0021	≤ 0.482
66% ^d	≤ 0.00867	≤ 0.701	≤ 0.01196	≤ 0.705	≤ 0.0120	≤ 0.705
100%	≤ 0.03728	≤ 0.794	≤ 0.04588	≤ 0.797	≤ 0.0463	≤ 0.797

HR, hazard ratio; NA, not applicable; OS, overall survival.

^a Analyses of OS will be conducted at 5% alpha level only if the null hypotheses for both the primary and secondary PFS endpoints are rejected prior to testing OS.

^b OS will not be tested at the 33% information fraction unless the null hypothesis for PFS has been rejected.

^c The interim analysis at 33% information fraction will be conducted at 4% alpha level.

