7.2 Control of Type I Error

Inflation of Type 1 error associated with testing of multiple-primary endpoints and a secondary efficacy endpoint (PFS between single-agent cabozantinib and control) will be controlled by a modified Bonferroni procedure and a parallel gatekeeping method (FDA 2017). Initially, the study-wise 2-sided alpha of 5% will be unequally allocated between primary endpoints PFS (1%) and OS (4%). The secondary PFS endpoint will be tested at the 1% level only if the primary PFS test is successful. If the null hypotheses are rejected for both the primary and secondary PFS endpoints, the 1% alpha for PFS will be reallocated to OS, allowing it to be tested at the 5% level.

Two interim analyses of OS are planned at the 33% and 66% information fractions (the first interim will coincide with the primary analysis of PFS and will be performed only if the null hypothesis for PFS is rejected analysis and is expected to occur at approximately the 33% information fraction). Type 1 error associated with interim analyses will be controlled using Lan-DeMets O'Brien-Fleming (LD-OF) alpha-spending functions based upon a 4% total alpha allocation for OS. However, if the null hypotheses are rejected for both the primary and secondary PFS endpoints, the 1% alpha for PFS will be reallocated to OS per the fallback method. As a consequence, the final OS analysis will employ critical values from the spending function at 5% level. The alpha level of the interim analysis at 66% will be dependent on the timing of the interim analysis. It can be conducted at 5% alpha level only if it occurs after the null hypothesis for the secondary PFS is rejected. (see Section 7.3).

All other statistical evaluations of efficacy will be considered exploratory.

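### Protocol 9.5 gives the final OS test both 4% and 4.96% total alpha when the second OS interim precedes a successful final secondary PFS analysis, and Protocol 9.8 and SAP 7.2 say 5%

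*Protocol*

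**What the plan says.** Protocol 9.5 splits alpha as 1% for primary PFS and 4% for OS. If primary PFS and then secondary PFS are both rejected, the 1% passes to OS. On OS looks: "Two interim analyses of OS are planned at the 33% and 66% information fractions".

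Item c.ii covers a non-significant secondary PFS interim. It first says "The final analysis of secondary PFS will be conducted at an alpha of 0.0096", and that the alpha of later OS analyses depends on both the timing and the result of that final analysis. Two rules then follow:

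- "The second interim analysis and the final for OS will be conducted per LD-OF with 4% alpha, if the second interim analysis occurs prior" (meaning ahead of final secondary PFS). The same 4% applies if that analysis comes first and fails.
- "The subsequent OS analyses will be conducted per LD-OF with 4.96% alpha if it occurs after the rejection of the null hypothesis for secondary PFS".

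Protocol 9.8 says that if both PFS nulls are rejected, "the final OS analysis will employ critical values from the spending function at the 5% level". SAP 7.2 agrees: "the final OS analysis will employ critical values from the spending function at 5% level". Footnote d to the boundary table in Protocol 9.8 settles the level for the 66% look only. SAP 7.3 allows the 5% values for OS analyses performed after secondary PFS is rejected, and its Table 11 has no 4.96% column.

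**The concern.** Take this sequence: second OS interim (IA2), then final secondary PFS rejected, then final OS. The condition in the first rule is only that IA2 came before the final secondary PFS analysis. That is met, and the rule names the final OS analysis as well as IA2, so the final OS is held at 4%. The second rule covers any OS analysis after the rejection. The final OS is one, so it gets 4.96%. Sections 9.8 and SAP 7.2 give 5%.

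The larger question is whether alpha is recycled to the final OS at all on this path; 4.96% against 5% makes little difference. An OS result between the two thresholds would succeed under one rule and fail under the other, on a primary endpoint. A choice made after seeing that result would be open to challenge.

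**Working it through.** **Boundaries.** Inputs (Protocol 9.7 and 9.8): 368 deaths, 2:1 allocation, Lan-DeMets O'Brien-Fleming spending, looks taken at 123, 245 and 368 deaths. For two-sided total α, the cumulative spend per side at information t is 2[1 − Φ(z₁₋α/₄ / √t)]. Boundaries are solved from the joint normal distribution of the looks, with HR = exp(−z / √(D × 2/9)). At 368 deaths √(368 × 2/9) = 9.043.

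The plan's 4% column is reproduced first: p = 0.00011, 0.00867, 0.03728, with final HR = exp(−2.0827/9.043) = 0.794. (With looks at exactly 33% and 66%, the final p is 0.0374.)

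| Final OS rule | Final critical p | HR at 368 deaths |
|---|---|---|
| 4% throughout | 0.0373 | 0.794 |
| 4% at both interims, total 4.96% | 0.0474 (z = 1.9831) | 0.803 |
| 4% at both interims, total 5% | 0.0478 (z = 1.9794) | 0.803 |
| Printed 4.96% column | 0.04588 | 0.802 |
| Printed 5% column | 0.0463 | 0.802 |

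The printed columns assume the larger spend at the earlier looks. Used after two looks at 4%, they give totals of about 4.81% and 4.85%, within 4.96% and 5%. (The HR of 0.797 printed beside them fits about 348 deaths, not 368.)

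**Order of the looks.** Inputs: 30 subjects per month, OS medians 17.8 and 12.3 months, PFS medians 5.5 and 3.6 months, exponential times. No dropout rate is stated; zero is assumed. With accrual rate r over [s, e] and λ = ln 2 / median, expected events by month T are r{(e − s) − [exp(−λ(T − e)) − exp(−λ(T − s))]/λ}, replacing e by T while accrual continues.

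For 740 subjects at 2:1:1 this gives final OS at 38.2 months (stated 38) and the 283rd secondary PFS event at 25.3 (stated 25). The plan gives no date for IA2. Solving for 0.66 × 368 = 242.9 deaths gives 26.5 months. At 25.3 months there are about 226 deaths, 61% information. So under Table 33 the final secondary PFS comes first, and there 9.5 is clear.

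SAP section 3 reports 837 subjects, 188 of them single-agent, and enrolment began at 6:3:1. Assuming one switch to 2:1:1 after x subjects, 0.10x + 0.25(837 − x) = 188, so x ≈ 142. No document states this figure.

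| Scenario | IA2 (months) | Final secondary PFS (months) | IA2 first? |
|---|---|---|---|
| Table 33: 740, 2:1:1, 30/month | 26.5 | 25.3 | No |
| 740, 25/month | 29.4 | 29.1 | No |
| 740, 20/month | 33.7 | 34.8 | Yes |
| 740, no OS effect (12.3 both arms) | 23.9 | 25.3 | Yes |
| 837 with switch, 30/month | 25.5 | 26.1 | Yes |
| 837 with switch, 25/month | 28.4 | 30.2 | Yes |
| 837 with switch, 35/month | 23.3 | 23.2 | No |
| 837 with switch, 40/month | 21.6 | 21.0 | No |

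**How often it would decide the trial.** At secondary PFS HR 0.65, with the interim boundary that fits the plan's HR limit of about 0.626, the chance of rejecting at the interim is 0.393 and overall 0.851. Failing and then succeeding has probability 0.851 − 0.393 = 0.46. The chance that OS passes both interims unrejected and ends with p between 0.0373 and 0.0474 is about 1.6% at HR 0.69 and 3.8% at HR 0.80. Treated as independent, the products are about 0.7% and 1.7%, before requiring primary PFS success and this order of looks.

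**The case against.** The best defence is that nearly every other statement points to recycling. The synopsis, the opening of 9.5, Protocol 9.8 and SAP 7.2 all move the 1% to OS once both PFS nulls fall, SAP 7.3 is worded analysis by analysis, and 9.5 itself makes later OS alpha depend on the result of the final secondary PFS analysis. Read in order, the second rule updates the first, and only the mention of the final analysis in the first rule is out of step. That stands as evidence of intent, so a reader who infers that the threshold is undefined goes too far: it is defined more than once. It does not remove the conflict, because the first rule names the final OS analysis and no clause says which rule prevails.

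Three other stronger readings are tempting. One is that the plan's own rates predict this order; Table 33 gives the reverse. The reported enrolment reverses it by only 0.6 to 0.7 months, on a back-solved switch, and accrual of 35 per month or more restores it. The second is that Type I error is inflated; holding OS at 4% is conservative, and 4.96% or 5% stays within the recycled total. The third is that the printed larger-alpha boundaries are invalid here; they are slightly conservative, and both documents say actual critical values depend on the actual information fraction.

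It is also fair that keeping 4% once IA2 has been run at 4% would be a valid rule. The documents need one rule, and either would control error.

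**Conclusion.** The point holds as an inconsistency in the primary OS decision rule on one branch: primary PFS significant, secondary PFS interim not significant, IA2 before the final secondary PFS analysis, and that analysis then significant. The final OS critical p is about 0.037 (HR 0.794) on one reading and 0.0474 to 0.0478 (HR 0.803) on the other if the boundary is re-solved. The conflict changes the conclusion only for a final p in that band, an event of roughly 1% to 2% or less under the assumptions shown.

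The boundary figures rest on looks near 33% and 66% of 368 deaths. The timing rests on exponential medians, constant accrual and no dropout; the 837-subject case adds the assumed switch. The disputed order is plausible with the reported enrolment, slower accrual or a smaller OS effect, but it is not the planned one.

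**What to change.** Before OS data are seen, state one rule for this branch and use it in Protocol 9.5 and 9.8 and in SAP 7.2 and 7.3. The version consistent with the plan's stated recycling is:

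- In item c.ii, remove the final OS analysis from the 4% rule where only IA2 precedes the final secondary PFS analysis, leaving that rule to govern IA2.
- State that the final OS uses the recycled total if secondary PFS is rejected before it, and give that total once, as 4.96% or 5%, in all four sections.
- Keep looks already taken at their 4% spend, and solve the final boundary from cumulative alpha spent.
- If the sponsor prefers to hold OS at 4% once IA2 has been run, say so, and amend 9.8 and SAP 7.2 and 7.3 to match.

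The cost is a wording change in the protocol and SAP and one boundary calculation. Sample size, event targets and data collection are unaffected.
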